Exploratory Aim 2: Validate the BACtrack Skyn wrist-worn alcohol sensor device against the industry standard Alcohol Monitoring Systems (AMS) Scram ankle-worn alcohol sensor device, as well as alcohol diary self-monitoring. We will conduct sensitivity/specificity analysis as well as linear regression comparing estimated blood alcohol level (BAL) after adjustment for covariates that may impact transdermal alcohol concentration including gender, body mass index (BMI), skin temperature, and physical activity levels.

2. **Probable Duration of Project:** State the expected duration of the project, including all follow-up and data analysis activities.

It is expected that the study will take 3 years to conduct and analyze.

3. **Background:** Describe the background information that led to the plan for this project. Provide references to support the expectation of obtaining useful scientific data.

Alcohol use disorder (AUD) onset peaks during young adulthood (i.e., 18-25).⁽¹⁾ Compared to older adults, young adults report more frequent and heavier alcohol consumption that is linked to substantial negative consequences including risk of accidental injury, the primary cause of death among young adults.⁽²⁻⁴⁾ Current alcohol intervention strategies for young adults have modest effects⁽⁵⁻⁷⁾ and young adults rarely self-identify for specialized alcohol treatment.^(8, 9) Thus, more work is needed to identify effective alcohol interventions and novel treatment engagement strategies to reduce this substantial public health burden.

HIC # 2000021048

One novel approach is to target poor sleep, a common complaint among young adults who drink heavily^(10, 11) and an AUD risk factor in young adults.⁽¹²⁻¹⁴⁾ Sleep problems in young adults may be due to important developmental changes in sleep that begin with puberty and continue into young adulthood. During this developmental period, there is a need for more sleep⁽¹⁵⁾ and a preference for later bed and wake times,⁽¹⁶⁾ which often conflict with school/work demands and social/cultural obligations.⁽¹⁷⁾ To cope with these conflicts, adolescents and young adults may maintain shorter, more variable sleep schedules putting them at-risk for sleep problems, excessive daytime sleepiness, and other negative consequences.⁽¹⁷⁻¹⁹⁾

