In our preliminary study of a mobile sleep intervention for heavy-drinking young adults (N=42), all participants demonstrated adequate adherence to sleep-monitoring activities. Adherence was defined as wearing the sleep tracker 75% of the time and completing 75% of the daily sleep diaries (i.e., 5 days). Adequate adherence during baseline sleep monitoring was a requirement for randomization. Only 1 out of 43 individuals was excluded prior to randomization for not adhering during this baseline period. Of those randomized (N=42), all demonstrated adequate adherence. In our qualitative study to inform initial intervention development, young adults expressed interest in emerging mobile technologies that provide an objective assessment of alcohol consumption.⁽³⁴⁾

4. **Research Plan:** Summarize the study design and research procedures using non-technical language that can be readily understood by someone outside the discipline. **Be sure to distinguish between standard of care vs. research procedures when applicable, and include any flowcharts of visits specifying their individual times and lengths.** Describe the setting in which the research will take place.

We will be conducting a study that will examine improved sleep as an effective treatment target for reducing AUD risk in young adults.

Screening, Intake, and Randomization (Week 0): Participants who meet internet screening eligibility criteria will attend an in-person intake at one of our study sites (the SATU clinic of the Connecticut Mental Health Center (CMHC) located at [name], the main offices of the CMHC located at [name], or the Yale School of Nursing Biobehavioral Lab located at [name]) to learn

HIC # 2000021048

about the study, provide informed, voluntary consent, be further evaluated for eligibility, and complete baseline assessments. If found eligible, participants will be randomly assigned (stratified by gender) to 1 of 3 treatment conditions: Treatment Condition 1: Participants receive only web-based sleep hygiene advice (A); Treatment Condition 2: Participants receive web-based sleep hygiene advice + sleep/alcohol diary self-monitoring (A+SM); Treatment Condition 3: Participants receive web-based sleep hygiene advice + sleep/alcohol diary self-monitoring + sleep/alcohol data feedback (A+SM+F).

[REDACTED]	[REDACTED]	[REDACTED]	[REDACTED]	[REDACTED]
[REDACTED]	[REDACTED]	[REDACTED]	[REDACTED]	[REDACTED]

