[REDACTED]	[REDACTED]	[REDACTED]	[REDACTED]	[REDACTED]
[REDACTED]	[REDACTED]	[REDACTED]	[REDACTED]	[REDACTED]
[REDACTED]	[REDACTED]	habits	[REDACTED]	[REDACTED]

[figure not shown]
A randomization ratio of 2:1:1 (stratified by gender) will be used to assign participants to conditions. Specifically, we will enroll twice as many participants in A+SM+F condition compared to the other 2 conditions. The larger sample will allow us to better evaluate the types of sleep/alcohol data feedback that young adults find helpful and acceptable. There are three types of sleep data: (1) quantitative sleep characteristics from the sleep tracker and sleep diary (e.g., sleep duration, sleep efficiency, percent awake, bed/wake times), (2) self-report ratings of sleep quality and sleepiness/sleep-related impairment upon

waking; and [REDACTED]. In addition, there are two types of alcohol data: (1) estimated blood alcohol level from the alcohol tracker and (2) self-reported alcohol consumption from the sleep diaries. The research assistant will demonstrate how to wear the Respiromics Actiwatch Spectrum Plus, the AMS Scram blood alcohol tracker, the Skyn Sensor blood alcohol tracker, how to access the sleep and alcohol diaries, and arrange to pick up the Actiwatches, AMS and Skyn Sensor blood-alcohol trackers, and chargers at the end of each 7-day monitoring period. To encourage compliance, we will compensate participants for each day that they complete daily sleep dairies.

Treatment Phase (Weeks 1-2): For 2 weeks following randomization, participants in all 3 conditions will wear a Respiromics Actiwatch Spectrum Plus sleep tracker, an AMS Scram blood alcohol tracker, and a Skyn Sensor blood-alcohol tracker daily. Those assigned to the 2 conditions that involve sleep/alcohol diary self-monitoring (i.e., A+SM; A+SM+F) will complete daily mobile application-based sleep diaries during the 2 weeks following intake.

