[REDACTED] the end of the first seven-day monitoring period, the research assistant will pick up the Actiwatch Spectrum Plus sleep tracker and a AMS Sensor blood-alcohol tracker from the participant. Upon receipt of the sleep trackers, we will download participants' scored sleep and alcohol use data from the prior week to include in the web-based sleep hygiene program and tailor the take-home health tips handouts that participants will receive the next day at each in-person visit. The next day the participant will return for an in-person visit and will receive empirically-supported brief sleep hygiene advice via the web-based program from our prior study. [REDACTED]

Follow-Up Phase: (Weeks 4, 8, 12): Participants will attend a 1 follow-up visit at each of these time points for a total of 3 follow-up visits: Weeks 4, 8, and 12 after starting treatment. At these visits, participants will complete a number of questionnaires that will ask about and assess sleep, mood, health behaviors, alcohol use, psychological characteristics, and will complete a computer task (See Table 3 Variables/Measures below). Participants will also be asked about their use of the tailored health tips based on their sleep data and whether any of the sleep tips were helpful.

Figure 1: Study Flow Chart

[figure not shown]

Table 4: Variables/Measures

Variables	Assessments	Intake	Diary Self-Monitoring	Alcohol/Sleep Trackers	Weeks 1, 2, 4, 8, 12
Eligibility/ Lab/ Medical	Demographics	X			
	DSM-V Diagnoses	X			
	Urine Drug Screen	X			

	Breath Alcohol	X			X
	AUDIT	X			
	Endorse Sleep Concerns	X			
	Height and weight	X			
	Physical Fitness Survey	X			
Alcohol Outcomes	Timeline Followback	X			X
	Alcohol-Related Consequences	X			4, 8, 12
	AMS Tracker Blood Alcohol Level			X	
	Skyn Tracker Blood Alcohol Level			X	
	Drinking Self-Monitoring Log		X		
Sleep Outcomes	PROMIS™ Sleep-related Impairment	X			4, 8, 12
	PROMIS™ Sleep Disturbance	X			4, 8, 12
	Pittsburgh Sleep Diary		X		
	Psychomotor Vigilance		X		
	Positive and Negative Affect Scales	X			4, 8, 12
	Munich Chronotype and Horne-Ostberg Morningness/Eveningness	X			
	Actiwatch: sleep onset/offset; total sleep time; sleep efficiency; % awake			X	
Self-Control	Stop Signal Task	X			4
Working Memory	N-Back Task	X			4
Behavioral Mechanisms	Behavioral Intentions Questionnaire (2 items)	X			
	Global Attitudes Scale	X			
	Subjective Norms Questionnaire	X			
	Drinking Refusal Self-Efficacy Questionnaire	X			4, 8, 12

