Sleep Concerns. Participants will be asked at screening if they are concerned about their sleep using a dichotomous item (i.e., yes/no) developed for our initial study. Positive endorsement is an inclusion criterion.

[figure not shown]
NIH PROMIS™ Sleep-Related Impairment is a validated, reliable measure of perceived alertness, sleepiness, and tiredness during waking hours and functional impairments due to sleep problems.⁽⁶³⁾ Participants' scores can be compared to national norms. The PROMIS-SRI will be assessed at intake and Weeks 4, 8, and 12.

NIH PROMIS™ Sleep Disturbance is a validated, reliable measure of perceived sleep quality/satisfaction and difficulty initiating/maintaining sleep.⁽⁶³⁾ Participants' scores can be compared to national norms. The PROMIS-SD will be administered at intake and Weeks 4, 8, and 12.

Positive and Negative Affect Scales is a validated, reliable 20-item measure of positive and negative mood that yields a total score for positive and negative moods respectively.^[88] The PANAS will be assessed at intake and Weeks 4, 8, and 12. Sleep improvement may cause mood changes that could affect alcohol outcomes.

Munich Chronotype/Horne-Ostberg Morningness-Eveningness Questionnaires are reliable, valid assessments of participants' chronotype and morning/evening preference that will be administered at intake.⁽⁶⁵⁾

Pittsburgh Sleep Diary is a well-validated assessment of daytime sleep-related behaviors and nocturnal sleep characteristics.⁽⁶⁶⁾ Participants assigned to conditions that include sleep self-monitoring will complete daily mobile application-based Pittsburgh Sleep Diaries in the mornings to track daytime sleep-related behaviors and nocturnal sleep characteristics of the preceding day. Diaries will include questions about caffeine and alcohol use as well as ratings of sleep quality and sleepiness upon waking. These are included in the same mobile application as the DSML described on the previous page.

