[name] will apprise fellow investigators and study personnel of all UPIRSOs and adverse events that occur during the conduct of this research project. [name] will hold weekly study meetings with investigators to review study progress, including any adverse events. Investigators who are not present at these meetings will be alerted via email by [name].

The protocol's research monitor(s), e.g., the Yale IRB and NIH will be informed of *any adverse events that meet these 3 criteria: (1) unexpected, (2) related/possibly related to study participation, and (3) places subjects or others at greater risk of harm than previously known/recognized*. These adverse events will be reported within 48 hours of the event becoming known to [name].

13. Statistical Considerations: Describe the statistical analyses that support the study design.

The goal of the Primary Aim is to examine the effect of sleep condition over time on total drinks consumed over Weeks 4-12, controlling for baseline total drinks. For this analyses, we will evaluate changes in scores using a mixed model repeated measures analysis with sleep condition and sex as between-subject factors and time as a within-subject factor. We will also test changes in secondary alcohol outcomes: drinks per day, drinks per drinking day, alcohol-related consequences, and estimated blood alcohol level, controlling for baseline alcohol outcomes, for which we will adjust for multiple comparisons. A mixed model will account for the correlation in alcohol outcomes measured in the same individual and will allow us to use all available data on individuals. The best-fitting variance-covariance structure will be selected using Schwartz-Bayesian Information Criterion (BIC). Time will be considered as a categorical factor but we will also evaluate whether alcohol outcomes change linearly by sleep condition over time. Where appropriate, we will apply transformations (e.g. log) to the dependent measures to comply with model assumptions or we will employ alternative methods (i.e. resampling, nonparametric tests). Expected Results: We hypothesize that participants in the A+SM+F condition will demonstrate the greatest reductions in total drinks of all 3 conditions which will correspond to significant group by time effects with significant between-group differences in change from baseline to end-point.

Statistical Analyses for Secondary Aim

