The goal of the Secondary Aim 1 is to examine the effect of sleep condition on sleep quality ratings over time, controlling for baseline ratings. We will use mixed model repeated measures analysis as described above. We will also test changes in secondary sleep outcomes: ratings of sleep-related impairment and sleep quantitative outcomes (i.e., duration, efficiency, % awake, bed/wake times), controlling for baseline responses. Expected Results: We hypothesize that participants in the A+SM+F condition will demonstrate the greatest improvements in sleep quality of all 3 conditions which will correspond to significant group by time effects with significant between-group differences in change from baseline to end-point.

For Secondary Aim 2, we will use descriptive statistics to summarize participants' acceptability ratings of web-based sleep hygiene advice, sleep/alcohol diary self-monitoring, sleep/alcohol tracker use, and personalized sleep/alcohol data feedback. We anticipate that the A+SM+F condition will yield the highest acceptability ratings of all 3 conditions. A review of participants' reactions to personalized sleep feedback will provide insight into what types of feedback and tailored health tips are feasible and useful for heavy-drinking young adults.

For Exploratory Aim 1, we will evaluate improvements in sleep quality over time and self-control (i.e., Stop Signal Task performance), working memory, and behavioral processes as mechanisms of sleep condition effects on total drinks at Month 3. We will calculate individual slope change estimates for sleep quality and then evaluate these slope estimates as potential mechanisms using a SAS macro outlined by Valeri and VanderWeele. (69) This method allows for independent variable X mediator interactions and is suitable for count outcomes (i.e., total drinks). Given the smaller sample size for this exploratory research, we will then evaluate correlations between

HIC # 2000021048

sleep quality slope estimates and self-control rather than use structural equation modeling to model potential complex pathways among sleep condition, sleep quality, self-control, and drinking.

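### Chronotype is measured at intake in every arm but enters no analysis; using it would sharpen the actigraphic bed- and wake-time comparisons at almost no cost

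*Combined protocol and SAP*

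**What the plan says.** - **Measurement.** Section I, item 4 (Sleep and Sleep-Related Characteristics) describes two instruments that assess "chronotype and morning/evening preference that will be administered at intake". Table 4 lists them as "Munich Chronotype and Horne-Ostberg Morningness/Eveningness", marked at Intake only and tied to no arm.
- **Timing.** At the intake visit (Screening, Intake, and Randomization) participants "complete baseline assessments. If found eligible, participants will be randomly assigned (stratified by gender) to 1 of 3 treatment conditions". The scores therefore precede allocation and exist in all three arms.
- **Outcomes.** Item 13 (Secondary Aim 1) will test "sleep quantitative outcomes (i.e., duration, efficiency, % awake, bed/wake times), controlling for baseline responses".
- **Model.** Secondary Aim 1 takes over the primary model, a "mixed model repeated measures analysis with sleep condition and sex as between-subject factors and time as a within-subject factor".
- **Tracker wear.** Under Treatment Phase (Weeks 1-2): "For 2 weeks following randomization, participants in all 3 conditions will wear a Respiromics Actiwatch Spectrum Plus sleep tracker". Table 4 has no Intake mark for the Actiwatch, and Section VI, item 2 pays for at most 14 days of wear.
- **Other roles.** The mediation aim lists sleep quality, self-control, working memory and behavioral processes. The device-validation aim lists gender, BMI, skin temperature, fitness and activity. The exclusion criteria mention marijuana and caffeine as possible moderators or mediators. Chronotype is in none of these lists.

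**The concern.** A measure of morning/evening preference is an obvious candidate predictor of when people go to bed and get up. It is collected from everyone, before allocation, and then left unused in the models for those outcomes. Whatever spread it would explain stays in the error term and widens the intervals for the arm differences.

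The usual reply is that the outcome's own baseline already does this work. That reply is weak for the tracker outcomes. The 14 paid days equal the two weeks after randomization, and daily sleep diaries are assigned only to the two self-monitoring arms. The visible text thus offers no pre-randomization bed or wake time from the tracker, and no diary value for the advice-only arm. What is at stake is the precision of some secondary comparisons, not their validity.

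**Working it through.** The documents give no power calculation, effect size or SD, so there is no figure to reproduce.

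**Inputs from the documents.** Up to 140 participants (Section I, item 6), allocated 2:1:1 (item 4): 140/2 = 70 in A+SM+F and 140/4 = 35 in each of A+SM and A.

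**Assumptions.** Two-sided 5%, 80% power, no dropout, one average value per participant. The correlation r between the chronotype score and actigraphic bed or wake time, within arm and sex, is not in the documents; 0.3–0.6 is shown.

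**Case 1: no outcome baseline in the model.** The standard error is multiplied by √(1 − r²). The detectable difference in SD units is (1.960 + 0.842) × √(1/n₁ + 1/n₂) × √(1 − r²).

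- 70 v 35, unadjusted: 2.802 × √(1/70 + 1/35) = 2.802 × 0.207 = 0.58
- 35 v 35, unadjusted: 2.802 × √(1/35 + 1/35) = 2.802 × 0.239 = 0.67

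| r | √(1 − r²) | SE reduction | 70 v 35 | 35 v 35 | Equivalent N, 140/(1 − r²) |
|---|---|---|---|---|---|
| 0 | 1.000 | 0% | 0.58 | 0.67 | 140 |
| 0.3 | 0.954 | 4.6% | 0.55 | 0.64 | 154 |
| 0.4 | 0.917 | 8.3% | 0.53 | 0.61 | 167 |
| 0.5 | 0.866 | 13.4% | 0.50 | 0.58 | 187 |
| 0.6 | 0.800 | 20.0% | 0.46 | 0.54 | 219 |

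A simulation of 4,000 trials at 70:35:35 with arm and sex in the model gave SE reductions of 3.9% at r = 0.3 and 12.4% at r = 0.5, and a loss of 0.5% at r = 0.

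**Cost of the extra term.** With 140 − 4 = 136 residual degrees of freedom, the variance inflation is about 1 + 1/(136 − 2) = 1.0075. Break-even is r = √(1 − 1/1.0075) ≈ 0.09.

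**Case 2: an outcome baseline is in the model.** What counts is then the partial correlation given that baseline. Let ρ be the baseline–outcome correlation (assumed 0.5–0.8), with chronotype equally correlated with both. The partial correlation is p = r(1 − ρ)/√[(1 − r²)(1 − ρ²)], and the further SE reduction is 1 − √(1 − p²).

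| ρ | r | p | Further SE reduction |
|---|---|---|---|
| 0.5 | 0.3 | 0.182 | 1.7% |
| 0.5 | 0.6 | 0.433 | 9.9% |
| 0.8 | 0.3 | 0.105 | 0.6% |
| 0.8 | 0.6 | 0.250 | 3.2% |

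The direction is the same in both cases. The size depends heavily on whether a usable baseline exists.

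**The case against.** The strongest case against is that omitting an optional prognostic covariate is not an error. The comparison stays valid under randomization, other intake measures are also absent from these models, and bed/wake times are one item in a list of secondary outcomes. All of that stands, and it makes this a low-priority improvement.

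A second objection is that the plan already controls for baseline responses, so the marginal correlation overstates the gain. That is right wherever such a baseline exists, and Case 2 gives the smaller figures. But the visible text shows none for the tracker. The baseline monitoring period under Preliminary Studies belongs to the previous trial. Week 1 wear could be pressed into service, but it follows randomization, when two arms are already keeping diaries. Some treatment-phase text is redacted, so a baseline arrangement cannot be wholly excluded, although the 14 paid days leave no paid week for it.

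Stronger readings that a reader might infer, and that the documents do not support:

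- *Chronotype explains most of the variation in bed and wake times.* No figure is given; the assumed range means r² of only 9–36%. The Background's remark on "a preference for later bed and wake times" describes a developmental shift shared by the age group, not spread between people within an 18–25 sample.
- *Chance chronotype imbalance biases the comparison.* It does not, under randomization. The unadjusted standard error already reflects it, so counting it separately would state the same loss twice.
- *Sleep duration should be adjusted too.* Nothing in the documents links chronotype to duration.

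**Conclusion.** The point holds as a modest gain in precision. Chronotype is available before randomization in every arm, is used nowhere, and is the closest listed intake proxy for actigraphic bed and wake times.

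If r is 0.3–0.6, leaving it out forgoes an SE reduction of about 5–20% when no outcome baseline is in the model, or about 0.6–10% when a baseline correlated 0.5–0.8 with the outcome is present. It would be tempting to quote the larger range whatever is decided about a tracker baseline; only the direction is that robust. These sizes rest on an r that the documents do not give, and the detectable differences also rest on assumed power, alpha and full retention. Neither the primary total-drinks analysis nor the main sleep-quality outcome is affected.

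**What to change.** In item 13, Secondary Aim 1, prespecify one intake chronotype score as a covariate in the models for actigraphic bed time and actigraphic wake time only. State which of the two questionnaires supplies it, so that the choice cannot be made after the data are seen. In the same place, say what the baseline response is for tracker outcomes, since the value of the covariate depends on it.

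The cost is a line or two of analysis text and one degree of freedom in each of the two models, repaid once r exceeds about 0.09. No new data, visits or participant burden are needed.

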With the exception of our preliminary work, the question of whether improving sleep reduces drinking and alcohol-related risks has only been tested in older adults.^(27, 28) In older populations, poor sleep is a well-established alcohol relapse risk factor⁽²⁹⁻³²⁾ but sleep interventions have yielded mixed results.^(29, 33) One challenge for treating sleep problems among older adults with AUDs is that chronic, heavy alcohol exposure can have substantial negative effects on sleep that can persist for two or more years following abstinence.⁽³²⁾ Therefore, it may be more effective to target sleep problems earlier during young adulthood before these negative sleep-alcohol cycles become entrenched. Another potential advantage of sleep interventions is that heavy-drinking young adults are open to information to help them sleep better⁽³⁴⁾ and sleep interventions address alcohol use as standard care.⁽³⁵⁾ In our proposed research, we will evaluate whether daily sleep/alcohol self-monitoring + sleep hygiene advice is more effective than sleep hygiene advice alone as well as whether providing personalized feedback based on diaries and sleep/alcohol trackers can lead to further improvements in alcohol outcomes and the mechanisms by which this may occur. The ultimate goal of this research is to examine improved sleep as an effective treatment target for reducing AUD risk in young adults. We will randomly assign participants to 1 of 3 web-based sleep/alcohol self-monitoring + sleep/alcohol data feedback intervention conditions: (1) web-based sleep hygiene advice; (2) web-based sleep hygiene advice + sleep/alcohol diary self-monitoring; or (3) web-based sleep hygiene advice + sleep/alcohol diary self-monitoring + sleep/alcohol data feedback for two weeks of treatment and monitoring followed by 3 follow up visits. We will measure changes in alcohol consumption and sleep quality in order to address the following aims:

Primary Aim: Examine the effect of sleep condition over time on total drinks consumed over Weeks 4-12, controlling for baseline total drinks. The primary alcohol outcome will be change over time in total drinks consumed. Secondary alcohol outcomes will include changes in total drinks per day, drinks per drinking day, alcohol-related consequences, and estimated blood alcohol levels from the alcohol tracker. We hypothesize that participants in the A+SM+F condition will demonstrate the greatest reductions in total drinks of all 3 conditions

HIC # 2000021048

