Timeline Follow-back Interview (TLFB) is a standardized, validated, and reliable experimenter-administered interview that will be used to obtain quantity and frequency estimates of alcohol consumption for a 30-day period prior to enrollment in the study and monthly following intake for a total of 3 months.⁽⁵¹⁾ Calendar prompts and memory aids (e.g., holidays) are used to facilitate accurate recall of substance use during the targeted period. We will derive the following 30-day summary variables from the TLFB for intake and Weeks 4, 8, and 12: total drinks, drinks per day, drinks per drinking day.

Alcohol-Related Problems will be assessed at intake, Weeks 4, 8, and 12 using the Young Adult Alcohol Consequences Questionnaire (YAACQ), a reliable, valid measure of 48 consequences that may have occurred due to alcohol consumption that are predictive of drinking persistence among young adults.⁽⁶²⁾

Drinking Self-Monitoring Log (DSML) is a standardized, validated methodology for measuring drinking on a daily or drink by drink basis. Participants assigned to conditions that include self-monitoring will complete daily mobile application-based DSML diaries in the mornings to track drinking behaviors of the preceding day. [REDACTED]

[REDACTED]

[REDACTED]

Blood Alcohol Concentrations during at-home assessment will be determined using the AMS Scram alcohol tracker, an ankle-worn biosensor, and Skyn Sensor alcohol tracker, a wrist-worn alcohol biosensor, which both provide continuous measures of participants' blood alcohol levels. The AMS Scram device is downloaded to a docking station weekly, and the Skyn device works with a smartphone to track this data. We will turn off access to the data so that participants do not receive immediate feedback about their blood alcohol levels. We will also set up the applications so that they are not directly linked to participants but rather to their participant numbers. Data is downloaded to secure, password-protected servers administered by AMS and Skyn Sensors respectively. Any data stored on the device will be immediately deleted after download. We will download the data using our research computers after collecting the devices from participants.

[REDACTED]

Sleep and Sleep-Related Characteristics:

HIC # 2000021048

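### The Primary Aim names no primary test, levels of time or role for baseline, and the group-by-time effect it is tied to is a poor test of a sustained benefit

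*Combined protocol and SAP*

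**What the plan says.** Section I.13 (Statistical Considerations) gives the Primary Aim as to "examine the effect of sleep condition over time on total drinks consumed over Weeks 4-12, controlling for baseline total drinks". The model has "sleep condition and sex as between-subject factors and time as a within-subject factor". On the form of time it adds: "Time will be considered as a categorical factor but we will also evaluate whether alcohol outcomes change linearly by sleep condition over time".

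The hypothesis, in Sections I.1 and I.13, is that A+SM+F will show the largest reductions, "which will correspond to significant group by time effects with significant between-group differences in change from baseline to end-point". Sleep quality (Secondary Aim 1) gets the same sentence in both sections.

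Other wording bears on the role of baseline. Section I.13 says "we will evaluate changes in scores using a mixed model repeated measures analysis". Section I.1 says "The primary alcohol outcome will be change over time in total drinks consumed". The Timeline Follow-back entry in Section I.4 says "We will derive the following 30-day summary variables from the TLFB for intake and Weeks 4, 8, and 12: total drinks".

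The levels of time are not listed, and baseline is not named as a model term. The week meant by end-point is not given, although Exploratory Aim 1 in Section I.13 refers to total drinks at Month 3. No single test or pairwise comparison is designated primary. Section I.1 asks more than one question of the three arms, including "whether daily sleep/alcohol self-monitoring + sleep hygiene advice is more effective than sleep hygiene advice alone".

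**The concern.** Two readings are open, and the wording supports both.

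- **Baseline as covariate.** Analysing Weeks 4-12 while controlling for baseline suggests that time is Weeks 4, 8 and 12. Group-by-time then asks whether the arm difference changes between those visits. A benefit present by Week 4 and held to Week 12 appears in the condition effect and not in the interaction. The linear-by-condition analysis has the same limit.
- **Intake as a level of time.** The references to change, and the total derived at intake, suggest four levels. Group-by-time then includes the step from intake and can detect a held benefit, but it spreads that benefit over 6 degrees of freedom and does not adjust for baseline.

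The hypothesis sentence is the only stated link between the aim and a test. A sustained benefit, which is the result the investigators would want, could come with a non-significant interaction that readers take as failure to confirm. With no result named in advance, the choice among the interaction, the condition effect, the linear trend and the end-point comparison stays open until the data are seen.

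**Working it through.** The plan gives no power calculation, so there is no figure to reproduce.

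**Inputs from the documents.** Up to 140 participants (Section I.6); 2:1:1 allocation favouring A+SM+F (Section I.4), so 35/35/70; total drinks at intake and Weeks 4, 8 and 12.

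**Assumed, because the documents are silent.** Two-sided 5%; normal data; compound symmetry with correlation r = 0.4 to 0.7; no dropout; effect d = 0.5 or 0.3 SD for A+SM+F against A, with A+SM either midway between them or equal to A. All tests below are three-arm omnibus tests, so they are compared like for like.

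**Between-arm spread.** S = Σ n(δ − mean δ)². At d = 0.5:
- A+SM equal to A: the mean is −0.25, and S = 140 × 0.0625 = 8.75.
- A+SM midway: the mean is −0.3125, and S = 35(0.3125²) + 35(0.0625²) + 70(0.1875²) = 6.016.

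**Noncentrality λ for a constant benefit.** Ranges run from S = 6.016 with r = 0.4 to S = 8.75 with r = 0.7.
- Group-by-time, baseline as covariate (4 and 274 df): λ = S × Σ(p − mean p)²/(1 − r), where p is the visit profile of the benefit. With p = (1, 1, 1), λ = 0 and power equals alpha for any d, N or r.
- Group-by-time, intake as a level (6 and 411 df): p = (0, 1, 1, 1), so Σ = 0.75. λ runs from 6.016 × 0.75/0.6 = 7.52 to 8.75 × 0.75/0.3 = 21.9.
- Adjusted condition effect, average of three visits (2 and 136 df): variance (1 + 2r)/3 − r², which is 0.44 at r = 0.4 and 0.31 at r = 0.7. λ runs from 13.7 to 28.2.
- Adjusted condition effect at Week 12 (2 and 136 df): variance 1 − r², which is 0.84 and 0.51. λ runs from 7.16 to 17.2.

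For d = 0.3, each λ is multiplied by (0.3/0.5)² = 0.36.

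| Test, constant benefit | d = 0.5 | d = 0.3 |
|---|---|---|
| Group-by-time, baseline as covariate | 5% | 5% |
| Group-by-time, intake as a level | 49-96% | 19-52% |
| Adjusted condition effect, average of Weeks 4/8/12 | 92-99.8% | 49-81% |
| Adjusted condition effect, Week 12 | 66-97% | 28-59% |

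**If the Week 4 difference is diluted.** The Week 4 total covers 30 days and overlaps treatment Weeks 1-2. Taking Week 4 as day 28, 21 of the 30 days follow the first monitoring week (70%) and 14 follow the end of treatment (47%). With baseline as covariate, Σ(p − mean p)² = (2/3)(1 − w)², where w is the Week 4 fraction. This is 0.06 at w = 0.70 and 0.19 at w = 0.47. At d = 0.5, λ runs from 6.016 × 0.06/0.6 = 0.60 to 8.75 × 0.19/0.3 = 5.5, so power is about 8-43%. The averaged condition effect, with λ scaled by ((w + 2)/3)², keeps 77-99%.

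**Is a held benefit plausible?** Pilot Table 1 (Preliminary Studies) gives HB minus CIAN in change from intake. For typical-week drinks it is (13.63 − 18.16) − (16.34 − 17.95) = −2.92 at Week 5 and (8.56 − 18.16) − (11.15 − 17.95) = −2.80 at 3 months, almost flat. For heaviest-week drinks the same sums give −4.69 and then −6.76, a growing difference.

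**The case against.** The strongest reply is that the low-power reading fits the sentence badly. An interaction paired with change from baseline makes most sense if intake is a level of time, and then power at d = 0.5 is 49-96%. That has weight, but the stated aim of controlling for baseline over Weeks 4-12 points the other way, and the text does not settle it. On the favourable reading, the adjusted average still has more power at every setting computed.

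The 5% figure also needs an exactly constant difference. The schedule makes some Week 4 dilution likely and the pilot is mixed, so 8-43% may be the more realistic range on the covariate reading. That stands.

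The other figures depend on d and on compound symmetry, whereas the plan selects the covariance structure by BIC. That also stands. At d = 0.3 even the better tests are modest.

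A reader might infer that the trial cannot show benefit. It can: the end-point comparison in the same sentence detects a sustained benefit on either reading. A reader might also infer that success requires both the interaction and the end-point difference to be significant. The documents set no such rule; the sentence describes expected results, so no joint power is claimed here.

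**Conclusion.** The point holds as an under-specified primary analysis whose named interaction is a poor confirming test. The omission is plain from the text. With baseline as covariate, group-by-time is uninformative about a benefit held constant from Week 4, a result that needs no assumption about effect size, sample size or correlation. With intake as a level, the interaction works but loses power to the adjusted average: 49-96% against 92-99.8% at d = 0.5, and 19-52% against 49-81% at d = 0.3. Those ranges rest on 140 participants at 35/35/70, compound symmetry, correlation 0.4 to 0.7 and no dropout. This should be fixed before analysis; it does not invalidate the design.

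**What to change.** In Section I.13, with matching wording in Section I.1:

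- State that baseline total drinks enters as a covariate (or through a common baseline mean in a constrained longitudinal model) and that time is Weeks 4, 8 and 12.
- Name one baseline-adjusted between-condition result from the mixed model as primary, in place of group-by-time. It can be the 2-df condition effect or a named pairwise contrast, at Week 12 or averaged over Weeks 4, 8 and 12. The investigators choose.
- If more than one pairwise contrast is confirmatory, say how multiplicity is handled. Section I.13 mentions adjustment only with the secondary alcohol outcomes.
- Report condition-by-time and the linear trend as descriptions of persistence or fading.
- Do the same for sleep quality in Secondary Aim 1.

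The cost is SAP wording only, with no new data or visits. The trade-off is that averaging includes a Week 4 total that partly covers the treatment weeks, while Week 12 alone has less power.
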